# 11.5.18 Exploratory Endpoint – Anti-tumor Activity and Changes in PSA - Prostate Cancer Subjects Only

This section defines the endpoints used to address the assessment of anti-tumor activity and changes in PSA for the prostate cancer subjects. Depending on number of prostate cancer subjects treated in the escalation part, the summaries of the prostate cancer-specific endpoints in the escalation part may be omitted.

#### 11.5.18.1 Modified ORR

For the prostate cancer subjects the modified ORR (mORR) is defined as confirmed response in soft tissue (visceral or nodal disease), per RECIST v1.1 (Eisenhauer et al., 2009), with no evidence of bone progression according to the Prostate Cancer Working Group 3 (PCWG3) criteria. The mORR is defined as the proportion of subjects with either complete or partial response.

The estimated mORR and the exact 2-sided 95% CIs using the Clopper-Pearson method will be presented for the prostate cancer subjects. Individual subject data listings will be provided.

#### 11.5.18.2 Modified DCR

Modified DCR (mDCR) is defined similar to the definition in Section 11.5.10.2, but based on the response modification defined in Section 11.5.18.1.

The estimate of the mDCR and the exact 2-sided 95% CIs using the Clopper-Pearson method will be presented the prostate cancer subjects. Individual subject data listings will be provided.

#### 11.5.18.3 Modified Duration of Response

Modified DOR (mDOR) is defined as the time from CR or PR (based on the response modification defined in Section 11.5.18.1) to the date of rPFS (see definition in Section 11.6.19.5). Censoring rules as described in Section 11.5.10.3 will be applied.

The mDOR distribution will be estimated using the Kaplan-Meier method, and the survival curve, median and 95% CI of the median will be presented. Individual subject data listings will be provided.

Version: 4.0

#### 11.5.18.4 Composite Response Rate

The composite response rate (CRR) is defined as a response per the modified RECIST v1.1 criteria *or* a PSA response (see Section 11.5.18.5).

The estimated CRR and the exact 2-sided 95% CIs using the Clopper-Pearson method will be presented for the prostate cancer subjects. Individual subject data listings will be provided.

# 11.5.18.5 Exploratory Endpoint - PSA Response

Complete PSA response is defined as a decline in PSA of  $\geq$ 50% from baseline confirmed by a second PSA measurement 4 to 6 weeks later.

The PSA response rate defined as the proportion of subjects with a PSA response in the FAS will be reported with exact 2-sided 95% CIs using the Clopper-Pearson method. Individual subject data listings will be provided.

# 11.5.18.6 Exploratory Endpoint - PSA Progression

Disease progression by PSA is defined as an increase in the PSA concentration by  $\geq$ 25% above nadir (or baseline, if PSA never decreased below the baseline), with an absolute increase in the PSA level by 2 ng/mL, confirmed by a second value 3 or more weeks later.

The rate of PSA progression, defined as the proportion of subjects with a PSA progression in the FAS will be reported with exact 2-sided 95% CIs using the Clopper-Pearson method. Individual subject data listings will be provided.

# 11.5.19

## 11.6 Analysis of Expansion Part

#### 11.6.1 Primary Objective

The primary objective is to evaluate the ORR for each expansion cohort.

#### 11.6.2 Primary Endpoint – Objective Response Rate

ORR will be analyzed as described in Section 11.5.10.1.

## 11.6.3 Statistical Hypothesis, Model, and Method of Analysis

No formal statistical hypotheses are formulated in this trial. Any P-values will be considered as hypothesis generating results to be considered for future trials.

The estimated ORR and the exact 2-sided 95% confidence intervals (CIs) using the Clopper-Pearson method will be presented for each expansion cohort. Individual subject data listings will be provided.

The maximal response (maximal reduction in the sum of the longest diameter in the target lesions) in target lesions at any time on trial will be reported using waterfall plots.

The results of the response as seen in the escalation part will be reported similarly.

#### 11.6.4 Handling of Missing Values/Censoring/Discontinuations

Any subjects with missing information regarding response to treatment will be counted as non-responders. Treatment of intermediate missing scans will be detailed in the SAP.

# 11.6.5 Supportive and Sensitivity Analyses

Not applicable.

# 11.6.6 Secondary Objectives

The secondary objectives are to:

- Evaluate anti-tumor activity (reduction in tumor size) based on response criteria relevant to the tumor type: DCR, DOR, and TTR.
- Evaluate efficacy, based on PFS and OS.
- Further describe the safety profile of GEN1044, based on AEs and safety laboratory parameters
- Further describe the PK profile
- Further describe the immunogenicity of GEN1044, based on ADA response.

# 11.6.7 Secondary Endpoint – Evaluation of Anti-tumor Activity

# 11.6.7.1 Disease Control Rate

DCR will be analyzed as described in Section 11.5.10.2.

#### 11.6.7.2 Duration of Response

DOR will be analyzed as described in Section 11.5.10.3.

## 11.6.7.3 Time to Response

TTR will be analyzed as described in Section 11.5.10.4.

# 11.6.8 Secondary Endpoint – Evaluation of Efficacy

# 11.6.8.1 Progression-free Survival

PFS is defined as the time from the date of C1D1 to the date of the first documented progression or death due to any cause. PFS will be assessed via local review according to RECIST v1.1 (Eisenhauer et al., 2009). PFS will be censored in accordance with Table C1 in Appendix C in the FDA Guidance for Industry: Clinical Trial Endpoints for the Approval of Non-small Cell Lung Cancer Drugs and Biologics (FDA-Guidance, 2015).

PFS will be analyzed in the FAS population. The PFS distribution will be estimated using the Kaplan-Meier method, and the Kaplan-Meier curves, medians and 95% CIs of the medians will be presented for each expansion cohort.

Version: 4.0

#### 11.6.8.2 Overall Survival

OS is defined as the time from date of C1D1 to date of death due to any cause. If a subject is not known to have died, then OS will be censored at the latest date the subject was known to be alive (on or before the cut-off date).

OS will be analyzed in the FAS population. The OS distribution will be estimated using the Kaplan-Meier method, and the Kaplan-Meier curves, medians, first and third quartiles and 95% CIs of the medians will be presented for each expansion cohort.

# 11.6.9 Secondary Endpoint – Adverse Events and Safety Laboratory Parameters

# 11.6.9.1 Analysis Set and Grouping for the Analyses

See Section 11.5.3.1.

#### 11.6.9.2 Adverse Events

See Section 11.5.3.2.

#### 11.6.9.3 Laboratory Abnormalities

See Section 11.5.3.3.

## 11.6.10 Secondary Endpoint – Pharmacokinetics

PK will be analyzed as described in Section 11.5.8.

# 11.6.11 Immunogenicity

Immunogenicity will be analyzed as described in Section 11.5.9.

# 11.6.12 Supportive Analyses of Secondary Efficacy Objectives and Endpoints

Not applicable.

#### 11.6.13 Other Safety Data

#### 11.6.13.1 Vital signs

See Section 11.5.12.1.

#### 11.6.13.2 ECGs

See Section 11.5.12.2. Single ECGs are planned for the Expansion part.

#### 11.6.13.3 ECOG Performance Status

See Section 11.5.12.3.

#### 11.6.14 Supportive Analyses for Secondary Objectives

Not applicable.

#### 11.6.15 Tolerability

Not applicable.

Version: 4.0

#### 11.6.16 Exploratory Objectives

#### 11.6.17 Exploratory Endpoint – Biomarkers

See Section 11.5.16.

# 11.6.18 Exploratory Endpoint – Anti-tumor Activity Based on iRECIST

See Section 11.5.17 where reference is made to iRECIST guideline (Seymour et al., 2017) and the exploratory endpoints iORR, iDCR and iDOR. In addition, the iPFS will be evaluated in the expansion cohorts, and presented similar to PFS, see Section 11.6.8.1. The event date for iPFS is the first date at which progression is met (provided that the progression is confirmed at the next assessment, with exceptions as described in Seymour et al., 2017) or date of death due to any cause, whichever comes first.

# 11.6.19 Exploratory Endpoint – Anti-tumor Activity and Changes in PSA – Prostate Cancer Subjects Only

See Section 11.5.18.

#### 11.6.19.1 Modified ORR

See Section 11.5.18.1.

#### 11.6.19.2 Modified DCR

See Section 11.5.18.2.

#### 11.6.19.3 Modified Duration of Response

See Section 11.5.18.3.

#### 11.6.19.4 Composite Response Rate

See Section 11.5.18.4.

#### 11.6.19.5 Radiographic Progression-Free Survival

Radiographic progression-free survival (rPFS) is defined as the time from the date of C1D1 to the date of the first documented progression per PCWG3-modified RECIST v1.1 (see Appendix 5, Table 25), or death due to any cause, whichever occurs first.

rPFS will be analyzed in the FAS population. The rPFS distribution will be estimated using the Kaplan-Meier method, and the Kaplan-Meier curves, medians and 95% CIs of the medians will be presented for the prostate cancer subjects.

# 11.6.19.6 PSA Response

See Section 11.5.18.5.

#### 11.6.19.7 PSA Progression

See Section 11.5.18.6.

Version: 4.0

#### 11.6.20

# 11.7 Operating Characteristics for the Interim Analysis in Expansion Cohorts

The maximum sample size for each expansion cohort is 40 subjects. In order not to expose subjects to non-efficacious doses, an ongoing and non-binding interim futility analysis will be conducted based on about the initial 20 subjects. The interim analysis will be conducted when (at minimum) 2 scans from these subjects in the expansion cohort have been locally reviewed. At this time point the confirmed ORR will be derived and used as endpoint in the futility analysis. Those subjects not yet confirmed (eg, last scan demonstrating a CR or PR) will be counted as SD (ie, non-responders). The analysis will be supplemented by secondary summaries of the response (at timing of futility analysis): ORR (based on unconfirmed responses), DOR, anti-tumor activity (changes from baseline in target lesion size), PFS, OS, summaries of PK concentrations and parameters, and safety assessments. The totality of the data will be evaluated by the sponsor SC, which decides on further recruitment into the expansion cohort.

The futility analysis will be based on a Bayesian predictive probability approach (Lee and Liu, 2008). By using predictive probabilities, it is possible to directly assess the outcome of the next stage, if continued to its end (Saville et al., 2014). Given the interim data, the predicted probability is a weighted average of posterior probabilities, as if calculated given the outcome at the end of the stage. The weights correspond to how likely each outcome is. The predictive probabilities may in fact be calculated at any time point.

At the end of the trial the *outcome* of interest, ie, the "success criteria," is defined as the posterior probability that ORR exceeds  $p_0$  is at least 70%. If the predicted probability of success at timing of interim is less than 10% the expansion cohort is judged futile.

The historical rates  $(p_0)$  are tabulated in Table 19. Based on these, the number of responders required at interim to continue are presented by indication in Table 20. In addition, given the prior response rate, the success criteria is translated into required number of responders.

The operating characteristics are based on 100000 simulations for each scenario and were programmed in R v3.5.1 using RStudio v1.2.1335 (R-Core-Team, 2018; RStudio-Team, 2018).

In this trial the prior response rate is modelled as  $Beta(1+p_0,1+[1-p_0])$ , which can be thought of as updating a uniform (non-informative) prior with a fraction of a response (ie,  $p_0$ ) from one subject.

Version: 4.0

The expansion cohorts are judged as successful (at n=20) under the target response rate. Assuming a historical response rate, the predictive probability of success (at n=20) fails to reach the 10% bar in about 12% to 24% of the cases.

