## 4.3 Expansion Part

In the Expansion part, subjects will receive the RP2D dose(s) determined from the Dose Escalation part. Depending on the RP2D, this will be a priming dose of GEN1044 on C1D1, an intermediate dose on C1D8, and then either a second intermediate dose or full dose on C1D15. In case of the implementation of a second intermediate dose on C1D15, the subject will receive the first full dose on C2D1.

An overnight stay (24 hours in-hospital observation) will be required for all subjects after administration of GEN1044 on C1D1. For subjects experiencing CRS or ICANS following GEN1044 administration on C1D1, additional 24-hour hospitalization will be required after administration of GEN1044 on C1D8. As data accumulate, increased (or reduced) hospitalization

Version: 4.0

may be implemented for additional subjects and/or dose administrations if recommended by the sponsor.

Based on data available and if deemed appropriate, the expansion may be initiated before a possible maximum tolerated dose has been reached. Furthermore, different doses and schedules might be explored in the expansion cohorts. The aim of the expansion is to provide further data on the safety, tolerability, MOA, PK and anti-tumor activity of the selected dose/schedule.

Recruitment will be initiated in up to 8 parallel cohorts in different tumor types. Expansion cohorts may include disease subtypes, eg, uterine, prostate, esophageal, head and neck, NSCLC/ACC, NSCLC/SCC, bladder and TNBC. In each of the expansion cohorts, a non-binding and ongoing interim futility analysis will be conducted after about 20 subjects have at least 2 on-treatment scans (approximately 12 weeks). A maximum of 40 subjects may be recruited in each expansion cohort.

Further expansion cohorts in additional tumor types may be opened based on preliminary efficacy signals generated in the Dose Escalation part. The sponsor will determine the priority of opening the disease-specific expansion cohorts based the data obtained in the dose escalation.

In the Expansion part, a DMC risk-benefit analysis will be performed at pre-specified intervals as defined in the DMC Charter. The DMC and the sponsor SC will evaluate the safety profile with particular emphasis on any safety signals. Additional details regarding the DMC can be found in Section 10.9.

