# 9.2.1.2 Post-Baseline Imaging Assessments

Imaging assessments as described in Table 13 should be performed at the time points specified using the same imaging modality used at baseline, irrespective of trial treatment interruption or actual dosing.

- Imaging assessments (CT/MRI) for response evaluation will be performed every 6 weeks (±7 days) after C1D1 during the first 36 weeks, and every 12 weeks (±7 days) thereafter, or more frequently if clinically indicated.
- For subjects with prostate cancer, bone scans will be performed every 6 weeks (+7 days) (or longer per local standards) during the first 24 weeks, and every 12 weeks (±7 days) thereafter.

Radiological/imaging assessments and bone scans should be scheduled using the first dosing date (C1D1) as the reference date (not the date of the previous tumor assessment) and should be respected regardless of whether treatment with trial treatment is temporarily withheld or unscheduled assessments performed. Radiological/imaging assessments and bone scans should continue until PD, the start of new anti-cancer therapy, the subject withdraws consent, or death, whichever occurs first. (In the case of PD per RECIST v1.1, treatment and imaging assessments may continue in clinically stable (non-prostate cancer) subjects per iRECIST; see below.)

Version: 4.0

Additional imaging assessments may be performed at any time during the trial at the investigator's discretion to support the efficacy evaluations for a subject. Clinical suspicion of disease progression at any time requires a physical examination and imaging assessments to be performed promptly rather than waiting for the next scheduled imaging assessment. Any imaging modalities, if obtained and clinically indicated to assess response or progression, must be entered in the electronic data capture (EDC) pages for evaluation of response or progression.

Each lesion that is measured at baseline must be measured by the same method and when possible, by the same local radiologist/physician throughout the trial so that the comparison is consistent. If an off-schedule imaging assessment is performed because progression is suspected, subsequent imaging assessments should be performed in accordance with the original imaging schedule.

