#### 11 STATISTICS

The Statistical Analysis Plan (SAP) will be developed and finalized before database lock and will describe the subject populations to be included in the analyses, and procedures for accounting for missing, unused, and spurious data. This section is a summary of the planned statistical analyses of the primary and secondary endpoints.

All presentations will be done separately for the Dose Escalation part and the Expansion part. Subjects in the Dose Escalation part will typically be analyzed according to the assigned DL cohort. Subjects in the Expansion part will be analyzed according to their assigned expansion cohort.

The primary analyses will be timed as follows:

- **Escalation**: Primary safety and efficacy analyses will be conducted on all subject data at the end of the escalation.
- Expansion: The expansion part consists of parallel cohorts, wherein each expansion cohort may report its individual primary analysis. Primary safety and efficacy analyses will be conducted on all subject data at earliest when all subjects who are still receiving trial treatment have at least 2 scans performed (such that the primary endpoint may be confirmed).

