**Table 19 Response Rate Characteristics by Indication** 

Case	Indication	Historical response rate (p 0 )
A	Head and neck, bladder, esophageal, TNBC	10%
В	NSCLC, prostate	15%
С	Uterine	35%

Table 20 Requirements on Number of Responders and Operating Characteristics

	Number of responders to achieve		Operating characteristics based on 100.000 simulations under true underlying ORR				
Case	Be judged as successful at n=20	A posterior probability of ORR that exceeds p 0 by at least 70% at final analysis	True ORR	Likelihood to not judge as successful at n=20	Likelihood that estimated ORR  ≥p₀ if final analysis is reached	Likelihood that posterior probability of ORR exceeds p 0 by at least 70% at final analysis	
A	>1/20	≥5/40	10%	12%	64%	41%	
			20%	1%	98%	93%	
В	B ≥2/20	≥7/40	15%	18%	66%	46%	
			30%	1%	99%	98%	
С	≥6/20	≥16/40	35%	24%	69%	39%	
			55%	1%	99%	98%	

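### The futility look scores responses awaiting confirmation as failures and Table 20's interim column allows for no such lag, so its 1% wrongful-futility figures are a best case

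*Protocol*

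**What the plan says.** Protocol Section 11.7 describes the rule as follows: "an ongoing and non-binding interim futility analysis will be conducted based on about the initial 20 subjects". The trigger is "The interim analysis will be conducted when (at minimum) 2 scans from these subjects in the expansion cohort have been locally reviewed". Section 4.3 puts the same trigger as "after about 20 subjects have at least 2 on-treatment scans (approximately 12 weeks". On the endpoint, Section 11.7 says "At this time point the confirmed ORR will be derived and used as endpoint in the futility analysis", and on responses without a confirmatory scan, "Those subjects not yet confirmed (eg, last scan demonstrating a CR or PR) will be counted as SD (ie, non-responders".

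Section 9.2.1.2 schedules imaging "every 6 weeks (±7 days) after C1D1 during the first 36 weeks". Section 11.5.10.1 requires the confirming scan to be at least 4 weeks after the response criteria are first met. Appendix 2 places it 4 to 6 weeks after.

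The column of Table 20 headed "Likelihood to not judge as successful at n=20" gives 12%, 18% and 24% at the historical rate p0 and 1% in all three cases at the higher ORR. It is described as simulated under a true underlying ORR. No time to response or confirmation delay is mentioned.

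For the primary analysis, Section 11 sets an earliest time: subjects still on treatment must "have at least 2 scans performed (such that the primary endpoint may be confirmed".

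**The concern.** A CR or PR first seen at Week 12 cannot be confirmed before about Week 16. If the look is run when the last of the 20 subjects reaches the second scan, that subject is a failure in the calculation whatever the next scan shows. Under Section 4.3 the first full dose falls on C1D15 or C2D1, so the Week 6 scan comes only about 4 or 3 weeks after it. Responses that first appear at Week 12 are therefore quite possible.

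The predictive probability refers to the outcome at 40 subjects, and these same 20 are among the 40. A pending PR may be a confirmed responder at the final analysis, yet the interim calculation fixes it as a non-response. This pushes the predictive probability down whenever a response is pending.

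What is at stake is the meaning of Table 20. It tells the sponsor Safety Committee that an effective cohort has a 1% chance of being judged futile, and the rule as written need not have that property.

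**Working it through.** **Inputs.** Table 19: p0 = 10%, 15%, 35% for Cases A, B, C. Table 20: higher (target) ORR = 20%, 30%, 55%. Section 11.7: interim n = 20, maximum n = 40, prior Beta(1+p0, 2−p0), success if the posterior probability that ORR exceeds p0 is at least 70%, futile if the predictive probability of success is below 10%.

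**Step 1: cut-offs.** The posterior probability at n = 40 is 0.607 with 4 responders and 0.775 with 5 (A), 0.580 with 6 and 0.731 with 7 (B), and 0.650 with 15 and 0.759 with 16 (C). The final cut-offs are therefore 5, 7 and 16, as in Table 20. The beta-binomial predictive probability at n = 20 is 2.2% with 0 responders and 15.6% with 1 (A), 4.1% with 1 and 18.5% with 2 (B), and 4.2% with 5 and 13.9% with 6 (C). The interim cut-offs are therefore c = 1, 2 and 6. Table 20 prints >1/20 for Case A. It must be read as at least 1/20: a cut-off of 2 would give 39% at p0 and 7% at target, not the stated 12% and 1%.

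**Step 2: reproduce the interim column.** P(stop) = P(X ≤ c−1), with X ~ Binomial(20, p).

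- Case A: 0.9^20 = 12.2% at p0; 0.8^20 = 1.2% at target.
- Case B: P(X ≤ 1) = 17.6% at p0; 0.8% at target.
- Case C: P(X ≤ 5) = 24.5% at p0; 0.6% at target.

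These match the stated 12/1, 18/1 and 24/1. The table therefore takes the interim response probability to be the full final ORR.

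**Step 3: allow for the lag.** Let f be the share of eventual confirmed responders already confirmed at the look. Replace p by f·p. For Case A at f = 0.8, the target figure is (1 − 0.16)^20 = 3.1% and the p0 figure is (1 − 0.08)^20 = 18.9%. The documents do not give f, so a range is shown.

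| f (assumed) | P(stop) at target ORR, A/B/C | P(stop) at p0, A/B/C |
|---|---|---|
| 1.0 | 1.2 / 0.8 / 0.6% | 12 / 18 / 25% |
| 0.9 | 1.9 / 1.6 / 2.3% | 15 / 23 / 36% |
| 0.8 | 3.1 / 3.0 / 6.6% | 19 / 29 / 50% |
| 0.7 | 4.9 / 5.7 / 15.6% | 23 / 36 / 64% |

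**Step 4: what drives f.** A 100,000-run simulation ran the look when the 20th subject reached Week 12, with confirmation at the next 6-weekly scan. It assumed first responses split 60/25/10/5% over Weeks 6/12/18/24. P(stop) at target for A/B/C was 4.6/5.2/14.1% with accrual over 12 weeks, 2.5/2.3/4.3% over 26 weeks and 1.8/1.4/2.0% over 52 weeks. The accrual times and the response split are illustrative assumptions.

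**Step 5: primary analysis at its earliest time.** As a worst case, suppose all 40 subjects are analysed at f = 0.8 with no interim. The chance of meeting the final criterion at target falls from 92/98/98% to 79/88/75%. Subjects enrolled earlier will have more scans, so the real effect would be smaller.

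**The case against.** Much can be said for the plan. Two scans is a floor. The look waits for about 20 subjects, so those enrolled earlier will usually have three or more scans, and with slow accrual the risk in Cases A and B stays near 1 to 2%. The look is described as ongoing and non-binding. Section 11.7 says predictive probabilities can be calculated at any time, puts ORR based on unconfirmed responses in front of the Safety Committee, and leaves the decision to the totality of the data. The lag also has a useful side: it raises stopping at p0, which Table 20 shows to be low. Using the confirmed definition at the interim, as at the final analysis, is a defensible choice.

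All of that stands, and it limits the size. It does not restore the stated operating characteristics. The unconfirmed ORR is a supplement and enters neither the predictive-probability rule nor Table 20. The higher stopping rate at p0 is a by-product of scan timing and is not reported either.

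A reader might infer from Section 11 that the protocol claims two scans confirm every response. It does not. The wording is permissive and sets only an earliest date, and the sentence scoring pending responses as SD belongs to the interim alone. For the primary analysis this is a timing risk, confined to an analysis run at or near the first permitted date.

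**Conclusion.** The point holds as a defect in the stated rule and its table. Table 20's arithmetic is correct for a look at which every eventual response is already confirmed, and Section 11.7 does not require that. The 1% figures are a best case and the 12/18/24% figures at p0 are too low, both by an amount the documents do not fix. Over an assumed 70% to 90% of responders confirmed, wrongful futility is about 2 to 5% in Case A, 2 to 6% in Case B and 2 to 16% in Case C. Case C (uterine) is the most sensitive.

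Two stronger readings are tempting. One is that the risk is really 12/18/52%. That needs only half of the eventual responders to be confirmed at the look, which nothing in the documents supports. The other is that effective cohorts would be closed at these rates. The percentages are chances of crossing a non-binding bar, with the unconfirmed responses also in view.

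SAP Section 2.2 states that no expansion data were collected, so this concerns the protocol design and affects no reported result.

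**What to change.** In Section 11.7, run the predictive-probability calculation only after any of the 20 subjects with a pending CR or PR has had the confirmatory scan, 4 to 6 weeks later. Alternatively, treat such subjects as pending and not as fixed non-responders. Align Section 4.3 with the choice.

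Re-run Table 20's interim column for that rule, at both p0 and target ORR, with a stated time-to-response and accrual assumption. Print Case A's interim cut-off as at least 1/20.

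In Section 11, set the earliest primary analysis so that any CR or PR pending at the cut-off has had its confirmatory scan. Include subjects who stopped treatment without radiographic progression, since Section 9.2.1.2 keeps them under imaging.

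The cost is a wording change and a short simulation, plus a delay of about 4 to 6 weeks for the few pending subjects. If pending responses are counted instead, some will fail to confirm, and an inactive cohort is somewhat more likely to continue. The re-run table should show by how much. The SAP no longer contains expansion analyses, so the changes belong in the protocol, or in any later protocol that reuses this design.
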